9.5 TREATMENT EMERGENT ADVERSE EVENTS (TEAE'S)

The frequency and percentages of subjects with treatment-emergent adverse events (TEAEs) will be tabulated by system organ class (SOC) and preferred term (PT), where treatment-emergent is defined as any AE with an onset on or after the first dose of study medication and through 30 days after the last dose of study medication or with an onset prior to the first dose of study medication that increases in severity on, or after the first dose of study medication and through 30 days after the last dose of study medication.

In addition, TEAEs that are considered at least possibly related to study treatment will be tabulated as well as deaths, SAEs, and events resulting in treatment discontinuation or termination. Additionally, the subset of events which occurred after the last study drug administration will be summarized.

9.6 ADVERSE EVENTS / SERIOUS ADVERSE EVENT CAUSALITY ASSESSMENT

The Investigator must also assess the relationship of any adverse event to the use of study drug, (whether none, one, or all) based on available information, using the following guidelines:

1. **Not Related:** Clear-cut temporal and/or mechanistic relation to a cause other than the study drug.
2. **Doubtful:** There is no reasonable possibility that the event is related to the study medications but a definite cause cannot be ascertained.
3. **Possible:** There is still a reasonable possibility that the cause of the event was the study medications but there exists a more likely cause of the event such as complications of progressive disease.
4. **Probable:** The most likely cause of the event is the study medications but other causes cannot be completely excluded.
5. **Definite:** Clear cut temporal and/or mechanistic relation to the study medications. All other causes have been eliminated. Events classified as definite will often be confirmed

by documenting resolution on discontinuation of the study medications and recurrence upon resumption.

In the summary of drug related AEs, “Not Related” and “Doubtful” will be considered as “Not Drug Related” and “Possible”, “Probable”, and “Definite” will be considered as “Drug Related.” In the event that causality is missing for an AE, it will be considered as “Drug Related.”

9.6.1 RECORDING OF ADVERSE EVENTS

All adverse events of any subject during the course of the trial will be reported on the electronic CaseReport Form, and the investigator will give his or her opinion as to the relationship of the adverse event to trial drug treatment (i.e., whether the event is related or unrelated to trial drug administration –ublituximab/IV placebo or teriflunomide/oral placebo). If the adverse event is serious, it should be reported as soon as possible and no greater than 24 hours to the sponsor or designee. Other untoward events occurring in the framework of a clinical trial are also to be recorded as AEs (i.e., AEs that occur prior to assignment of trial treatment that are related to a protocol-mandated intervention, including invasive procedures such as biopsies, medication washout, or no treatment run-in).

All AEs regardless of seriousness or relationship to ublituximab/IV placebo and/or teriflunomide/oral placebo treatment, as well as all pregnancies, spanning from the signing of the informed consent and until 20 weeks after discontinuation or completion of either protocol-specific treatment as defined by the protocol for that subject, are to be recorded on the eCRF/Pregnancy Report Form.

9.6.2 ABNORMAL LABORATORY VALUES AND VITAL SIGNS

The reporting of abnormalities of vital signs as adverse events should be avoided. Abnormalities of vital signs should not be reported unless any criterion for an SAE is fulfilled, the vital signs abnormalities cause the subject to discontinue trial treatment, or the investigator insists that the abnormality should be reported as an AE. Abnormal laboratory results should be noted in the eCRF as an adverse event if they are associated with an overdose, require prolong in-patient hospitalization, or are otherwise considered clinically significant by the investigator. If an abnormal laboratory value or vital sign is associated with clinical signs and/or symptoms, the sign or symptom should be reported as an AE, and the associated laboratory value or vital sign should be considered additional information that must be collected in the relevant eCRF. If the laboratory abnormality is a sign of a disease or syndrome, only the diagnosis needs to be recorded on the SAE Report Form or AE eCRF.

Clinical Laboratory Results will be summarized. Summary statistics for actual values and for changes from baseline will be tabulated for laboratory results by scheduled visit. Subjects with laboratory values outside of the normal reference range at any post-baseline assessment will be summarized, and graded per NCI CTCAE Version 4.03 when applicable. Subject incidence of laboratory toxicity will be summarized by treatment group and maximum grade for each laboratory test.

9.6.3 HANDLING OF ADVERSE EVENTS

All adverse events resulting in discontinuation from the trial should be followed until resolution or stabilization. Subjects must be followed for AEs for 20 weeks after discontinuation or completion of protocol-specific treatment. All new AEs occurring during this period must be reported and followed until resolution unless, in the opinion of the investigator, these values are not likely to improve because of the underlying disease or the subject is lost to follow up. In this case, the investigators must record his or her reasoning for this decision in the subject's medical record and as a comment on the eCRF. After 20 weeks, only AEs, SAEs, or deaths assessed by the investigator as treatment related are to be reported.

9.7 SERIOUS ADVERSE EVENTS

9.7.1 DEFINITIONS OF SERIOUS ADVERSE EVENTS

The definitions of serious adverse events (SAEs) are given below. The Principal Investigator is responsible for ensuring that all staff involved in the trial are familiar with the content of this section.

An SAE or reaction is defined as any untoward medical occurrence that:

- Results in death, is immediately life-threatening,
- Requires in-patient hospitalization or prolongation of existing hospitalization,
- Results in persistent or significant disability/incapacity, and/or
- Causes a congenital anomaly/birth defect.

Medical and scientific judgment should be exercised in deciding whether expedited reporting is appropriate in other situations, such as important medical events that may not be immediately life-threatening or result in death or hospitalization, but may jeopardize the subject or may require intervention to prevent one of the other outcomes listed in the previous definition. These should also usually be considered serious. Examples of such events are intensive treatment in an emergency room or at home for allergic bronchospasm; blood dyscrasias or convulsions that do not result in hospitalization; or development of drug dependency or drug abuse.

A SUSAR is defined as a suspected unexpected SAE, and SUSAR reporting is encompassed within SAE reporting guidelines as defined in this section.

Treatment within or admission to the following facilities is not considered to meet the criteria of "in-patient hospitalization" (although if any other SAE criteria are met, the event must still be treated as an SAE and immediately reported):

- Emergency Department or Emergency Room
- Out-patient or same-day surgery units
- Observation or short-stay unit
- Rehabilitation facility
- Hospice or skilled nursing facility
- Nursing homes, Custodial care or Respite care facility

Hospitalization due to MS relapse does not need to be reported to the Sponsor as an SAE if the Treating Neurologist medically confirms the relapse. The subsequent IRAP adjudication will not impact the reporting status of the SAE.

Events related to underlying MS disease (i.e., MS progression) also do not require reporting as an SAE.

Hospitalization during the trial for a pre-planned surgical or medical procedure (one which was planned prior to entry in the trial), does not require reporting as a serious adverse event to the Sponsor.

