4.2.3 INDEPENDENT RELAPSE ADJUDICATION PANEL (IRAP)

The IRAP will make all protocol-defined relapse determinations in this study. The IRAP will review all subject-reported, suspected, on-study relapses (i.e., new or worsening neurological symptoms) and all potential events are sent to the IRAP regardless of whether the Treating Neurologist considered the subject's symptoms to be the result of a relapse. Please see Appendix D, and Section 6.3.1 of this protocol, and the IRAP Charter for further details.

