- ≥ 2 points increase on one of the appropriate FS or 1 point on two or more of the appropriate FS. The change must affect the selected FS (i.e., pyramidal, ambulation, cerebellar, brainstem, sensory or visual). Note, the change in FS scores should correspond to the patient's symptoms (e.g., patient reported change in visual acuity should correspond to a change in the vision FS score). Episodic spasm, sexual dysfunction, fatigue, mood change or bladder or bowel urgency or incontinence will not suffice to establish a relapse;
- An increase of ≥ 0.5 points in the EDSS score (unless EDSS score = 0, then an increase of at least 1.0 points is required) from the previous clinically stable assessment.

MS relapses are defined as a new or worsening neurological symptoms lasting ≥ 24 hours with the absence of fever, injury, infection or adverse reactions to medications and accompanied by new neurological findings upon examination by the Examining Neurologist. The symptoms are attributed to MS and are preceded by 30 days of stability or improvement in neurological state. The change in EDSS score as assessed by the Examining Neurologist is ≥ 0.5 increase or ≥ 2 points increase on one of the appropriate FS or 1 point on two or more of the appropriate FS. The change must affect the selected FS (i.e., pyramidal, ambulation, cerebellar, brainstem, sensory or visual). Note, the change in FS scale scores should correspond to the patient's symptoms (e.g., patient reported change in visual acuity should correspond to a change in the vision FS score). Episodic spasm, sexual dysfunction, fatigue, mood change or bladder or bowel urgency or incontinence will not suffice to establish a relapse. Please note: sexual dysfunction and fatigue will not be scored. If the symptoms occur less than 30 days following the onset of a protocol defined relapse, it should be considered part of the same relapse and would not be treated with IVMP within the protocol. New or recurrent neurologic symptoms that evolve gradually over months should be considered disability progression, not an acute relapse and should not be treated with steroids.

The suspected relapse must be reviewed and confirmed by the IRAP; Appendix D. The IRAP will then notify the CRO and Treating Neurologist of the results of its review.

Treating Neurologist or designee will enter into the eCRF whether the neurological symptoms identified were a result of an IRAP-confirmed relapse.

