4.4.2 TREATING NEUROLOGIST MEDICALLY CONFIRMED RELAPSE

In suspected relapse events for which IRAP confirmation is pending, may not be logistically possible, and/or complete case profiles for IRAP review are not available, the Treating Neurologist will medically evaluate the suspected relapse event. In these cases, all information from the Treating Neurologist's medical evaluation should still be entered into the eCRF and provided to the IRAP for adjudication. This is to ensure each suspected relapse is documented. Treating Neurologist medically confirmed relapses will not be included in the ARR calculation for the primary endpoint. For any relapse that is Treating Neurologist medically confirmed, subjects should re-consent to continue participation in the trial.

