All MRI scans will also be reviewed locally by a radiologist for safety (identify any new clinical relevant abnormal MRI findings that are not consistent with the diagnosis of MS, with particular attention to the possibility of progressive multifocal leukoencephalopathy) and the MRI report will be provided to the Treating Neurologist/PI. After randomization, the MRI reports provided to the Treating Neurologist/PI will contain **only non-MS pathology**. At the investigational site, only the local radiologist/technician assigned to this study may have access to the MRI scan post-randomization; **the Treating Neurologist should not review the MRI scans unless a safety concern arises**.

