9 SAFETY REPORTING AND ANALYSIS

9.1 SAFETY ANALYSES

To evaluate the safety of ublituximab/placebo and teriflunomide/oral placebo, as determined by adverse events (AEs) and serious adverse events (SAEs), including MS worsening.

Safety will be tabulated as described below in the safety section. Tables will summarize the proportion of subjects ever experiencing a particular AE, and in select tables will also include the number of times a particular AE occurs.

Safety evaluations will be based on the incidence, intensity, and type of adverse events, as well as on clinically significant changes in the subject's physical examination, vital signs, and clinical laboratory results. Safety analyses will be performed using the safety population. Safety variables will be tabulated and presented by treatment actually received. Exposure to study treatment and reasons for discontinuation of study treatment will also be tabulated. Must obtain expert evaluations of brain MRI images of subjects with suspected opportunistic CNS infections including PML.

For select laboratory values, box plots of the values over time will be used for displays of these parameters. In the event of higher than expected incidence rates of abnormalities, further exploration of combinations of events, such as Hy's law, will be examined.

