Relapse determinations by the IRAP are communicated to the Treating Neurologist, who will in turn, notify the subject and update the eCRF accordingly. The IRAP has no involvement in subsequent subject management decisions. In order to maintain independence and blinding, the Examining Neurologist will not receive this report. Furthermore, neither the Treating Neurologist nor the subject may disclose the IRAP decision to the Examining Neurologist. The Treating Neurologist, upon receiving the IRAP decision, will counsel the subject per Section 4.4.1. The subject will need to give her/his consent to continue study participation.

For the Phase III study, the results of IRAP adjudications are transferred to the Sponsor only after the last subject completes the study. The Sponsor has no knowledge of IRAP adjudications while the study is ongoing.

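### Section 9.7.1 fixes the SAE exemption of a relapse hospitalisation before the IRAP has ruled, and nothing prompts the site to re-assess the event if the IRAP rejects it

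*Protocol*

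**What the plan says.** Protocol Section 9.7.1 sets the exemption: "Hospitalization due to MS relapse does not need to be reported to the Sponsor as an SAE if the Treating Neurologist medically confirms the relapse". Immediately afterwards the section fixes that status: "The subsequent IRAP adjudication will not impact the reporting status of the SAE".

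Section 4.4.2 says when a Treating Neurologist's medical confirmation applies: "In suspected relapse events for which IRAP confirmation is pending, may not be logistically possible", or when the case file for the panel is incomplete. So the opinion that grants the exemption can come before the panel's decision. Every suspected event still goes to the panel; Section 4.2.3 says that "all potential events are sent to the IRAP regardless of whether the Treating Neurologist considered" the symptoms to be a relapse.

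The relapse definition in Section 4.4.1 requires new or worsening symptoms "with the absence of fever, injury, infection or adverse reactions to medications". Appendix D binds the IRAP to that definition. It also says who hears the outcome: "Relapse determinations by the IRAP are communicated to the Treating Neurologist". Section 4.4.1 adds that the CRO is told and that the outcome is entered in the eCRF.

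Four other places bear on what happens if the event turns out not to be MS:

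- Section 9.6.1 has all AEs recorded, whatever their seriousness or relationship to treatment.
- Section 9.7.2 has non-serious AEs that become serious reported.
- Section 9.10 has a diagnosis established later reported as follow-up.
- Section 9.10.4 describes the hospitalisation exemptions, citing 9.7.1, as situations in which no AE has occurred. It also gives way to specific instructions elsewhere in the protocol.

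**The concern.** Exempting disease events from SAE reporting is a reasonable choice in a relapse trial. The difficulty is the point at which the exemption becomes final. It rests on a first opinion that may be formed before adjudication. A second assessment follows, against a written definition that excludes infection and drug reactions. When that assessment disagrees, 9.7.1 says the reporting status stands.

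An IRAP rejection is the one point described in the protocol at which the site is told that a hospitalised event did not meet the relapse definition. It is the natural moment to ask what the event was. As written, 9.7.1 invites the site to skip that question. If the true cause was an infection or a drug reaction, the event could stay out of expedited reporting and out of the serious-TEAE tables in SAP 2.4.5.1. It would also not count in the primary ARR, which uses IRAP-confirmed relapses only.

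**Working it through.** The point concerns a reporting rule, so there is no figure to reproduce. The check is to follow one hospitalised event through the text.

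1. **Admission.** A subject is hospitalised with new neurological symptoms. The IRAP decision is pending. The Treating Neurologist medically confirms a relapse (4.4.2). Under 9.7.1 the admission need not be reported as an SAE.

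2. **Adjudication.** The event goes to the IRAP (4.2.3, 4.4.2). The panel applies Section 4.4.1 (Appendix D). Its dossier includes AEs related to the event and any disqualifying features. It may reject the event on one of several grounds:
   - infection, fever, injury or an adverse drug reaction;
   - too small a change in EDSS or functional system scores;
   - symptoms lasting less than 24 hours;
   - less than 30 days of prior stability.

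   Only some of these point to a cause other than MS.

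3. **Notification.** The Treating Neurologist receives the decision (Appendix D), and the eCRF records whether the event was adjudicated as a relapse (SAP 2.1.3.1). Neither document says that the reason for rejection is sent.

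4. **After a rejection.** Two sets of text apply:
   - Section 9.7.1 says SAE status is unaffected.
   - Sections 9.6.1, 9.7.2, 9.10 and 9.10.4 would have the event recorded and reported *if* another diagnosis is established.

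   The second set depends on someone establishing that diagnosis. None of the four sections mentions an IRAP rejection, and no section asks the investigator to re-assess the cause when one arrives.

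5. **Consistency.** Section 9.10.4 describes the exemptions as cases without an AE. Section 9.7.1 keeps the exemption even where the rejected event was an AE. Because 9.10.4 defers to specific instructions, a site reading the two together could reasonably follow 9.7.1.

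6. **Where the event is still visible.** SAP 2.4.4.7 summarises days in hospital and the percentage of subjects hospitalised for suspected relapse, and SAP 2.4.4.10 analyses the proportion hospitalised. These are tertiary efficacy outputs, not safety tables, and they are not split by IRAP outcome.

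The size of the gap would need three rates: hospitalisation among suspected relapses, IRAP rejection among those the Treating Neurologist confirmed, and non-MS cause among the rejections. The documents give none of them.

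**The case against.** The strongest reply is that the harmful case is already covered. The exemption reaches only hospitalisation due to relapse, and it lifts a duty without forbidding a report. An infection or drug reaction is an AE, and once it is diagnosed, Sections 9.6.1, 9.7.2 and 9.10 require it to be recorded and reported. This stands, and it limits the point. A reader might infer from 9.7.1 that SAEs will be lost, or that sites are told to ignore a new diagnosis; the documents do not support either. What remains is that nothing starts the search for that diagnosis.

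A second reply is that a rejection often carries little information. The panel works from what the site entered and may not contact it, and many rejected events may still be MS. This also stands. It argues for re-assessment by the investigator and against automatic reclassification on the IRAP vote.

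A reader might also argue that the Treating Neurologist is poorly placed to judge because post-randomisation MRI reports are restricted. Section 6.3.3 points the other way. What is withheld is MS pathology; non-MS findings are passed on, after a local read "with particular attention to the possibility of progressive multifocal leukoencephalopathy". Section 9.1 further requires expert review of MRI where an opportunistic CNS infection is suspected.

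Third, Appendix D keeps IRAP results from the sponsor during the study, and an SAE report triggered by a rejection could disclose one. This is a fair constraint on the wording of a fix. It is met by reporting the re-assessed cause without citing the IRAP decision. The decision already goes to the CRO and into the eCRF, and it is not a treatment assignment.

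Finally, the DSMB sees unblinded relapse and EDSS data as well as AEs (synopsis, Study Design), and detailed SAE procedures sit in the Safety Monitoring Plan and the Investigator Study Guide, which are not available here. A re-assessment step may exist there. If so, 9.7.1 should still be made consistent with it.

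**Conclusion.** The point holds as a gap in procedure and an inconsistency between sections. Section 9.7.1 makes the exemption final on an opinion that may precede adjudication, infection and drug reaction are among the grounds on which adjudication can fail, and no text requires a second look when it does. Some hospitalised events rejected by the IRAP may therefore be reportable SAEs that are not reported.

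Its size is unknown. A reader might multiply the relapse count implied by the example ARR in Section 8.8 by guessed hospitalisation and rejection rates. That would not measure the gap. Confirmed relapses are properly exempt, and because the IRAP receives all suspected events, some rejected ones were never confirmed by the Treating Neurologist and so were never exempt.

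A reader might also infer that the loss differs by arm because fewer relapses are expected on ublituximab. The documents show neither a difference between arms in such misclassification nor its direction.

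The conclusion assumes that 9.7.1 is read as written and that no document outside the protocol and SAP adds the missing step. The change is worth making because it is cheap and concerns serious events. The text does not show that the SAE comparison is biased.

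**What to change.** 1. Reconcile Section 9.7.1 with Sections 9.10 and 9.10.4 by replacing the sentence on IRAP adjudication. Possible wording:

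   > *IRAP adjudication does not by itself change SAE status. If the IRAP does not confirm a relapse for a hospitalised event, the investigator re-assesses its cause and, if it is no longer attributed to MS, reports it as an SAE within 24 hours of that re-assessment, without citing the IRAP decision. An event already reported as an SAE stays reported.*

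   This keeps the exemption for IRAP-confirmed relapses and for rejected events the investigator still attributes to MS. It also keeps the existing protection for events already reported, and the 24 hours matches Section 9.7.2.

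2. At final analysis, tabulate hospitalisations for suspected relapse by arm and IRAP outcome beside the serious-TEAE table of SAP 2.4.5.1. The data are already collected for SAP 2.4.4.7 and for the primary endpoint. This would also put MS-related admissions in view of a safety evaluation that Section 9.1 describes "as determined by adverse events (AEs) and serious adverse events (SAEs), including MS worsening".

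The cost is one protocol sentence, one table and a few late SAE reports, some of which may prove to be MS after all. The re-assessment still rests with the investigator, so the change supplies the missing prompt but does not guarantee a different answer.
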